## HRP-503 - Template – Protocol

cluster randomized to either the MISC/WTM or WTM-only peer-led training standard of care. Randomization will occur by geographic location (i.e. village) rather than individually to minimize the likelihood of “spillover” (contamination and diffusion) effects within a community, whereby caregivers receiving training by a specialist provider might share aspects of their experience with caregivers receiving training from a peer-provider. Therefore villages participating in this study will be randomly assigned to peer- versus specialist-led group training intervention (randomized cluster technique). To maintain concealment of allocation, the randomization sequence will be generated by the trial biostatistician who is a full professor at MSU and very experienced at the clinical methodology and the statistical assessment of our study outcomes. She is the clinical methodologist and biostatistician for the konzo WTM non-inferiority R01 study, and will serve the same role in this study. Child neurodevelopmental and urinary thiocyanate and quality of home environment and evaluation of observed MISC interactions using the caregiving videos will be done by research assistants blinded to caregiver training intervention arm in the present study.

**C. Identify materials that will be used to recruit subjects (select all that apply):**

- None
- Letter, email, flyer, postcards, CD, DVD
- Newspaper, television, or radio advertisements
- Use of websites or Apps (e.g. Facebook, ResearchMatch)
- Other, describe if other is selected:

*CLICK IRB: Upload the recruitment materials to the Consent Forms and Recruitment Materials SmartForm page, Question 2.*

**D. The study team will obtain for the purpose of screening, recruiting, or determining the eligibility of prospective subjects (please select the appropriate option(s)):**

Not Applicable

- Information through oral or written communication with the prospective subject or legally authorized representative. Before the information is obtained for the purpose of screening, recruiting, or determining eligibility, consent:  will be obtained.  will not be obtained.  
*Please describe screening consent procedures in Question 13.*
- Identifiable private information or identifiable biospecimens by accessing records or stored identifiable biospecimens. Before the information is obtained for the purpose of screening, recruiting, or determining eligibility, consent:  will be obtained.  will not be obtained.  
*Please describe screening consent procedures in Question 13.*

*Note: The revised Common Rule permits an exception from informed consent for screening, recruiting, or determining eligibility when certain criteria are met; this exception does not apply to studies subject to the Pre-2018 Common Rule Requirements and/or studies regulated by the U.S. Food and Drug Administration (FDA).*

**1. Please explain your selection(s).**

Participation also requires receiving information on how to process cassava so that it is safe to eat. If and when the village tribal leader grants permission, groups of villagers will be invited to assemble and learn why the team has visited their village. The Kinshasa study team will repeat to the villagers the information previously provided to the tribal leaders. They will be encouraged to ask questions to which answers will be provided. Konzo will be familiar to the villagers, but they may not understand the causal connection between the consumption of cassava and the induction of walking difficulty. In particular, since cassava is a staple that provides a major source of nourishment that keeps them alive, there may be disbelief that a causal connection with disease could be possible. Other explanations for walking difficulties may be offered by the villagers, including punishment for undefined wrongdoing, a curse placed upon villagers by another tribal group, or the result of a natural event such as a flood or

a drought. Explanation that studies have shown that other people both near and far also develop “tied legs” if they do not wash their cassava roots for a sufficient period of time usually overcome doubts and focus attention on the principal cause of konzo. Great care must be taken to explain that cassava is an important and healthy food for the community provided it is properly prepared for human consumption. Since women of the village have major responsibility for food preparation and take pride in providing adequate nutrition for their family members, optimal food preparation is a subject of considerable interest and pride. Villagers will be familiar with the fact that children and women of childbearing age are the most heavily affected by konzo (relative to adult men), and it will therefore be logical that women and children are subjects of special importance to the study team.

**13. Consent Process.**

**A.** If the study involves adults, consent will be obtained from (select appropriate option(s)):  Not Applicable

- All subjects
- Some subjects
- No subjects (consent will not be obtained)

*CLICK IRB: Upload the consent document, script, etc. (including translations) to the Consent Forms and Recruitment Materials SmartForm page, Question 1.*

**B.** If the study involves children, parental permission will be obtained from (select appropriate option(s)):  Not Applicable

- Both parents or guardians (unless one parent is deceased, unknown, incompetent, or not reasonably available, or when only one parent has legal responsibility for the care and custody of the child)
- One parent or guardian
- Will not be obtained

*CLICK IRB: Upload the parental permission forms to the Consent Forms and Recruitment Materials SmartForm page, Question 1.*

**C.** If the study involves children, child assent will be obtained from (select appropriate option):  Not Applicable

- All children
- Some children
- Will not be obtained

*CLICK IRB: Upload the child assent form to the Consent Forms and Recruitment Materials SmartForm page, Question 1.*

**D.** Describe the consent process, including an explanation of your selection(s) above. If the study involves screening activities, please describe whether consent will be obtained and if consent will not be obtained, explain how the screening data will be used. If only some subjects will provide consent, explain who will or will not provide consent. If only some children will provide assent, explain which children will and will not provide assent.

Consenting will be performed by a member of the Kinshasa team on an individual basis after subjects have participated in the group meeting. Each subject will be asked to explain the purpose of the study: correct answers will be reinforced, and incorrect answers will be corrected with further information until the subject has a clear understanding. The subject will be informed they are free to accept or decline the invitation to participate and, if they choose to accept, they may withdraw at any time without recourse or penalty. Before making a decision whether to accept or decline, they will learn that participation in the study means the following: the study will have

access to the information being provided, as they provide a sample cassava flour, urine, and caregiver mental health/functionality and child neurodevelopment outcomes, for the study each time the research team visits the village over the course of the study period; answer some questions and provide a urine sample; be willing to learn about the MISC caregiver training intervention if chosen for that intervention arm in the study.

They are being told that their flour and urine samples will help the study team understand how to advise them on the best cassava preparation and risk for the disease konzo. They are also being informed that information collected from their blood/urine may be used in additional future studies of other diseases and their treatments. Participants will be encouraged to ask questions and, if necessary, take the necessary time to consider whether to participate or not. As noted in the research plan, after the first month of MISC training (under the supervision of experienced and Uganda certified MISC trainers at the Kahemba study site), the ten community women leaders trained to do the MISC trainers will continue to do bi-weekly personal MISC training sessions in the homes of the mothers to whom they have been assigned. One monthly encrypted and password protected videotaped MISC training session for each trainer will be uploaded to a secured DROPBOX for the remainder of the six-month MISC intervention period. These will be evaluated at our assessment center in Kampala Uganda for quality assurance and corrective feedback of the MISC training. We have used a similar procedure before for MISC training QA at our satellite study sites in rural areas of eastern Uganda, and the process worked well. A separate consent to video will be obtained from the mothers before the videotaping of any sessions, and the videotape will be available in a DROPBOX site that is only accessible to the trainers and the Ugandan MISC supervisors. Co-investigators Drs. [name] and [name], who have oversight for the MISC intervention portion, will also have access. All videotapes will be removed from the DROPBOX site and deleted within two weeks following evaluation for QA by the Ugandan MISC supervisors. This will all be explained in the separate consenting process of the mothers selected for the MISC training session videotaping with a given trainer for that month.

Agreement to participate will be taken if the child makes a clear statement of assent relevant for the present study, since all study children are under 7 yrs of age. The consent document will explain the purpose of the study, why questions will be asked, why flour and urine information is needed to be obtained for the study, the benefits and risks to the subjects, the payment schedule and amount, and the possibility of accepting or declining without consequence. There will be a clear statement that treatment of the disease will not be attempted and prevention of the disease cannot be assured. However, information will be provided in relation to the importance of knowledge to be gained and future intervention studies to prevent further cases of konzo. Subjects who agree to participate in the study will be asked to mark the consent document with an "X" by the side of the individual's name, as witnessed by the signature of the research assistant obtaining consent. They will also be asked for permission to record their face and their children(s) face photographically for the purposes of verification of the enrollee in future years. Whether permission for a photograph is granted or not, a unique number will be assigned to the enrollee and the number written on the document and photograph. Subjects who decide not to participate will not be asked to mark the document or to be photographed.

- E. If consent will not be obtained, explain why. Describe why the research could not be practicably carried out if consent was required. If the research involves identifiable private information or identifiable biospecimens, describe why the research could not practicably be carried out without using such information or biospecimens in an identifiable format.
- Not Applicable

- F. If your study involves use of a consent form, complete i, ii, and iii.
- Not Applicable

## HRP-503 - Template – Protocol

**i.** Select the appropriate option(s) below for the documentation of consent.

- Will use a written consent document signed by subjects
- Will use a short form written consent document signed by subjects
- Will not obtain a signed consent document for some subjects
- Will not obtain a signed consent document for all subjects

**ii.** Describe when and how the subject will receive a copy of the consent form.

A copy of the consent will be given to the caregivers after signatures are completed

**iii.** If subjects will not be signing the consent document, please explain why. If some subjects will not sign the consent document, explain who will and will not sign the consent.  Not Applicable

**G.** If the study involves cognitively impaired adults, explain the process to determine whether a subject is capable of consent, use of any legally authorized representative(s), and any assent process.  Not Applicable

*CLICK IRB: Upload any assessment tools to the Supporting Documents SmartForm page.*

### 14. Coercion or Undue Influence.

**A.** If some or all of the subjects are likely to be vulnerable to coercion or undue influence, such as children, prisoners, pregnant women, mentally disabled persons, individuals with impaired decision-making capacity, or economically or educationally disadvantaged persons, describe additional safeguards that have been included in the study.  Not Applicable

**B.** If you or your study team are associated with the subjects (e.g. your students, employees, colleagues, patients), explain the nature of any association and measures taken to protect subjects' rights, including safeguards against any coercion or undue influence (e.g. pressure a subject might feel to participate based on the association).  Not Applicable

### 15. Privacy.

How will subjects' privacy be protected? Consider the number of individuals interacting with the subject or subject's records, location of consent process and study, presence of individuals not associated with the study, sensitivity of the research.

The potential for loss of confidentiality is a serious threat that will take several training and procedural steps to minimize. The requirement of treating health information as confidential will be strictly emphasized for all staff as part of training prior to study initiation. All staff will be required to undergo certified training on human subjects' protection including the imperative of strictly adhering to confidentiality enhancing measures. All staff will be specifically trained to know that no one involved in this study is authorized to ever reveal/discuss participants' health information with third parties and that evidence of such violation will be associated with strict penalties including the loss of employment.

The first page of the risk-factor questionnaire, which contains identifying information, names and addresses, is removed after data entry and stored at INRB in a locked file dedicated to this

research study. The data files include only study numbers, which are linked through a security system, to a named file maintained for the purpose of informing individuals of information pertinent to their health. The name file is only accessible to the PI of the Kinshasa sub-contract (INRB), [name] (R01 PI), and [name] (R21 PI). The computer files are password-protected to ensure data security. All results will be reported in the aggregate. All data (including questionnaire, clinical, molecular) biomarkers are stored on a dedicated computer at INRB equipped with a back-up system. A tracking system will use unique ID numbers for all data files. These ID numbers will be used in the transfer of biomarker data and samples from the INRB to OHSU. Produced video/photo materials will be permanently kept by both the research team PI and the study participant. Flour cyanide and U-SCN surveillance date for the mother/child dyads, and neurodevelopmental and caregiver functionality mental health and HOME quality of caregiving data, all will be stored and managed in the MSU Biomedical Research Informatics Core (BRIC) secure server system (<https://ctsi.msu.edu/bric>) for access only by R21 PI [name] and Co-Investigators [name] (MISC and caregiver mental health) and [name] (biostatistician and clinical trial methodologist).

**16. Withdrawal of Subjects.** Not Applicable

If there are any anticipated circumstances where the researcher will withdraw subjects from the study regardless of the subject's wishes, describe the circumstances and the procedures when subjects are withdrawn from the study.

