Other caregiver/child assessments include video-taping of 15 minutes of child/caregiver interactions (5 minutes of caregiver feeding of child, washing of child, and work or play with child). These videos will be used on tablet as part of the MISC training, but also scored for observed mediational interactions in order to assess fidelity of MISC training and quality of caregiving. These video will be encrypted and password secured and will not be kept after the study, so as not to put the study identity of mothers and their children at risk. Mothers will consent to these videos as part of the informed consent process, and it will be a condition of eligibility for enrollment. This procedure with recording and scoring and management of videos was done for our Uganda-based clinical studies without adverse incidents or problems, and were clearly an important part of this type of caregiver training ECD intervention and assessment in a field-based clinical trial.

*CLICK™ IRB: Upload instruments (e.g. surveys, interview questions, questionnaires, etc.), measures, variables, etc. to the Supporting Documents SmartForm page.*

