**17. Monitoring Plan to Assess Data to Ensure Safety of Subjects.**

A. Is there a monitoring plan to periodically assess the data to ensure the safety of subjects or to ensure negative outcomes do not occur?

 No  
 Yes

Explain your answer. If you answered Yes, describe the monitoring plan.

The University of Kinshasa Neurology Department and the Oregon Health and Sciences University are presently maintaining a formal research collaboration, under the direction of [name] [name]. [name] is PI of the R01 randomized RCT for the wetting method prevention of konzo, within which the proposed R21 will be embedded. They are presently sponsoring the formation of a standing data safety and monitoring board based at the University of Kinshasa Medical School as part of ongoing NIH and CDC sponsored clinical trials research program. Clinical faculty members from the bioethics program at OHSU are supporting this effort in the formation of a DSMB for the R01 study. Also, the MSU Office of Clinical Research (OCR) within the Institute for Clinical and Translational Sciences is also committed to supporting the Thrive Early psychiatry global research initiative in the formation and support of any DSMB relevant to our efforts. For the MISC caregiver training clinical trials with HIV-affected households in Uganda, that provided regulatory guidelines and lists of key membership from our program in Epidemiology, Biostatistics, and Bioethics and Humanities for the DSMB for those clinical trials. In the meantime, the R21, R01, and Sub-Contractor (INRB) PIs will be responsible for monitoring any adverse events notably breach of confidentiality related to home-based MISC training, emotional duress for caregiver evaluation of mental health and caregiving functionality, and profound neurodisability for study children that becomes evident from this domain of outcomes assessment. Monitoring will be done on a continuous basis. Any adverse events will be reported to the Institutional Review Boards (IRB) of participating institutions to ensure that appropriate action is taken. This is an appropriate strategy because the proposed intervention for the present R21 proposed study is behavioral in nature and very low risk. Likewise, the outcomes assessments specific to this R21 are on-invasive lab (urine thiocyanate

levels) or behaviorally based and established to be low-risk from prior use in our preliminary assessment work in the DRC with konzo-affected households.

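### The Privacy section keeps video permanently, contradicting the separate deletion rules for interaction videos (Section 2) and training-session videos (Section 13)

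*Combined protocol and SAP*

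**What the plan says.** The protocol describes three kinds of identifiable image material and speaks about keeping them in several places.

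- **Interaction videos.** Section 2 (Procedures) describes 15 minutes of filming per caregiver and child, covering feeding, washing, and work or play. On retention it says the recordings "will not be kept after the study, so as not to put the study identity of mothers and their children at risk". On participation it says: "Mothers will consent to these videos as part of the informed consent process, and it will be a condition of eligibility for enrollment".
- **Training-session videos.** Section 13 (Consent Process), item D, has one MISC session per trainer uploaded each month to a restricted file-sharing site for QA review. It then says: "All videotapes will be removed from the DROPBOX site and deleted within two weeks following evaluation for QA by the Ugandan MISC supervisors". It adds that this will be explained in a separate consent with the mothers chosen for that filming.
- **Photographs.** Section 13 also asks permission to "record their face and their children(s) face photographically for the purposes of verification of the enrollee in future years". No deletion is promised. Section 5.C describes secure storage of the photograph with the other identifying details.
- **All of these together.** Section 15 (Privacy) says: "Produced video/photo materials will be permanently kept by both the research team PI and the study participant".

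Section 15 also says that "The potential for loss of confidentiality is a serious threat". Section 17 makes the investigators responsible for "monitoring any adverse events notably breach of confidentiality related to home-based MISC training".

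**The concern.** The recordings are among the most identifying material the trial will hold, showing mothers and very young children at home, some of it during washing. The protocol gives opposite instructions about how long they exist and who holds them. A team that follows the Privacy section keeps footage that Section 2 or Section 13 says will be gone. A team that follows Sections 2 and 13 breaches the Privacy section.

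This is more than loose drafting, for two reasons. Section 2 gives a reason for its rule, namely that keeping the footage would put the identity of mothers and children at risk, so permanent retention restores a hazard the protocol itself recognises. And for the training sessions, Section 13 says deletion will be explained to the mothers who consent, so keeping those recordings would break an undertaking given to participants.

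**Working it through.** No power, sample-size or error-rate figure bears on this point. The check is a comparison of the text, by type of material.

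| Material | Specific rule | Section 15 rule | Compatible? |
|---|---|---|---|
| Interaction videos | Not retained beyond the study (Section 2) | Permanent | No |
| Training-session videos | Deleted within two weeks after QA evaluation (Section 13.D) | Permanent | No |
| Photographs | Used to verify enrollees in later years, no deletion date (Section 13.D) | Permanent | Yes |

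**Step 1: do Sections 2 and 13 conflict with each other?** No. One governs home interaction recordings used for training and scoring. The other governs recordings of trainers at work, used for QA. Each can be followed without touching the other.

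**Step 2: does each conflict with Section 15?** Yes. The Privacy sentence names video and photo material together, says it is kept permanently, and carves out neither type of video. Neither a study-end limit nor a two-week limit can be met alongside permanent retention.

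**Step 3: do the holders agree?** Not for training sessions. Section 13.D restricts access to the trainers, the Ugandan supervisors and two co-investigators. Section 15 gives lasting copies to the research team PI and the participant.

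**Step 4: what reasons are given, and what are mothers told?** Only Section 2 gives identity protection as its reason. Only Section 13.D says deletion will be explained at consent, and only to mothers selected for training-session filming. Section 2 says mothers consent to the interaction videos but does not say they are told when those will be destroyed.

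**Step 5: who is affected?** Agreement to the interaction videos is an eligibility condition, so all 100 enrolled mothers and their filmed children fall under the first conflict. Section 12.B has the caregiving videos scored by assistants blinded to arm, which fits with filming in both arms. The second conflict can touch only the MISC/WTM arm (66 households), and within it only mothers selected for a filmed session.

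**The case against.** The strongest reply is that the Privacy sentence was never meant to cover these recordings. It stands among text on data storage and transfer between institutions, and may have been intended for photographs or other project media. On that view the specific rules in Sections 2 and 13 simply prevail. This is a plausible account of intent, but the sentence says video in plain terms and no other section narrows it. The reply supports correcting the sentence, not leaving it.

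It is also fair to say that the matter does not touch randomization, endpoints, power or analysis, and that correcting one sentence resolves it. Both points stand.

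Several stronger readings are tempting, and the documents do not support them:

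- A reader might infer three mutually incompatible rules. There are two compatible rules and one sentence that contradicts both.
- A reader might infer that the plan itself commits the breach that Section 17 monitors. Retention raises exposure but is not disclosure, and a mother holding her own footage has not disclosed it to anyone. Section 17's item is worded around home-based MISC training, and its place at the head of a list does not show priority.
- A reader might infer that every mother is promised destruction of her interaction videos. Section 2 does not say so, and the consent form is not among the documents reviewed.
- A reader might multiply 100 dyads by 3 assessment visits to get 300 recordings. Section 2 gives no filming schedule, so the count is unknown, and the point does not need it.
- A reader might infer that footage outlasts safety monitoring. Section 17 describes continuous monitoring and gives no end date.

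**Conclusion.** The contradiction is real and applies to both types of video. As written, the Privacy section defeats the protection that Section 2 gives to interaction videos. For training-session videos, it also defeats what Section 13 says mothers will be told.

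The scope is all 100 mothers for the interaction videos and a subset of the MISC/WTM arm for the training sessions. The conflict does not extend to photographs, where later use is foreseen and deletion is nowhere promised.

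The conclusion rests on reading the Privacy sentence as it stands, with video included. If the sponsor intended something narrower, the correction is the same. This is an internal inconsistency in participant protection that should be corrected, ideally before consent is taken, and it has no bearing on the trial's statistical conclusions.

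**What to change.** Remove video from the permanent-retention sentence in Section 15 and limit that sentence to the verification photographs described in Section 13. Then state one rule for each type of video, in one place, with cross-references:

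- Interaction videos are not kept past study end, and blinded scoring is completed before they are destroyed (the Section 2 rule).
- Training-session videos are deleted within two weeks after QA evaluation (the Section 13 rule).

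Section 21, item B, which asks how long identifiable material needs to be held, is a natural place for these rules. Check that the main consent and the separate video consent say the same thing.

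The cost is small. The protocol change is about a paragraph. Interaction videos could not be re-scored after the study closes, a limit Section 2 already accepts. If any consent wording changes, it needs translation and back-translation (Section 19.E) and review by the local IRB (Section 19.D).
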